## KING'S College LONDON

#### STUDY PROTOCOL

#### 5.2. Cluster randomisation

#### 5.2.1. Intervention arm - Opportunistic offering of self-sampling

GP practices randomised to the intervention arm will have an alert set up on their electronic patient record (EPR) software to automatically flag potentially eligible women when their record is loaded. Specifically, EPR systems will be programmed to flag women aged 25-64 who are at least 6 months overdue cervical screening (i.e. no cervical cytology recorded in the past 3.5 years (if aged 25-49) or 5.5 years (if aged 50-64) and no codes for hysterectomy or amputation of cervix).

Doctors, nurses and healthcare assistants (HCA)/assistant practitioners (AP) will be asked to offer self-sampling kits to women who have been flagged when they consult for any reason. In practice, this will be done on a case-by-case basis at the discretion of the healthcare professional consulted (e.g. SSKs will not be offered to women who are terminally ill). The study invitation will comprise a brief conversation (~2 minutes) at the end of the consultation. Once eligibility has been confirmed, women who agree will be given a self-sampling kit.

A study template will be set up in the GP electronic patient record system. When eligible women are offered kits, the consulting health professional will use the template to record:

- 1) Whether or not the study kit was accepted.
- Study kit number (if accepted).
- Reason for declining (if applicable)

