#### 6.1. Sample labelling

#### 6.1.1. Opportunistically offered kits

Sample tubes will be pre-labelled with a Preventx 'SK' number and barcode (standard barcode or two-dimensional barcode/Quick Response Code (QR code)). PSL will maintain a log of what 'SK' numbers were sent to each site.

The label will have space for the participant's name (first name and surname), date of birth and the date the sample was taken.

The GP, nurse or HCP handing out the kit will be required to write the 2 identifiers on the label (first name, surname and date of birth (DOB)) and will be required to affix the

Preventx barcode to the Lab Request/Consent form. Women will be required to write the date the sample was taken onto the swab label and laboratory request form (supplied by GP with participants name, address and DOB prepopulated).

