#### 8.1.1. Intervention arm – Opportunistic offering of self-sampling

With six GP practices randomised to the intervention arm, there would be some 4000 eligible women. Based on a previous study[19]) we estimate that 60% will consult their GP practice over one year, 500 (21%) will be opportunistically offered a self-sampling kit and  $\sim$ 330 (14%) will accept (4000\*0.60\*0.14). An estimated 210 (9%) (4000\*0.6\*0.09) would return a self-sample for HPV testing. Therefore, the proportion of women >6m overdue cervical screening who will return a sample when opportunistically offered a kit (i.e.  $\approx$ 210/2400) could be estimated with a 95% confidence interval of width  $\pm$ 1.0%.

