#### Opportunistic arm

- 1) Using electronic GP record searches: The proportion of eligible women who:
  - consult their GP practice
  - are offered a self-sampling kit
  - · accept a self-sampling kit
  - return an adequate self-sample.

We will also examine:

- 1) reasons why eligible women are not offered the self-sampling kit
- 2) reasons why eligible women decline self-sampling kits (if offered)

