#### 10.3. Opportunistic offering of self-sampling

GP primary care is a busy and time-pressured environment with an average GP consultation length of just 9 minutes.[22] In a previous study of opportunistic offering of self-sampling in GP primary care the consent procedure consisted of a brief (2 min) study explanation and verbal consent. This simplified approach was suggested by the reviewing REC committee (Brighton and Sussex NRES Committee 13/LO/1441) and worked well for the study with no issues raised. Therefore, we intend to use the same verbal consent procedure for this study. Consent to accept a self-sampling kit will be recorded in the women's GP medical record.

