### APPENDIX 1 – TABLE OF OBJECTIVES, ENDPOINTS & ASSESSMENT METHOD

Primary Objective	Endpoints	Assessment Method
To estimate the proportion of	Uptake of self-sampling	Opportunistic: number of eligible women with self-sample returned (using
women who provide a self-sample	within 6 months after	data provided by lab) as a % of total eligible women with Read codes for kits
when:	invitation	offered as per GP records
Offered kits opportunistically		vs
Sent a kit directly (opt-out)		Sent a kit directly (opt-out): number of women returned self-sample (using
Invited to order a kit (opt-in)		data provided by lab) as a % of total eligible sent kit directly
		vs
		Invited to order a kit (opt-in): number of women returned self-sample (using
		data provided by lab) as a % of total eligible sent letter (and separately for each
		method of kit ordering as a % of total eligible sent letter)
Secondary Objectives	Endpoints	Assessment Method
To estimate the proportion of	Attendance at follow up	Number of eligible women who test HPV positive on a self-sample and (i) have
women who test HPV positive on	(cytology or colposcopy)	codes for cytology or colposcopy attendance in their GP records within 6
a self-sample and attend for follow	amongst eligible women	months of HPV positive result and (ii) who have CIN2+ recorded in their GP
up within 6 months of a positive	within 6 months of testing	records; as a % of all eligible women who test HPV positive on a self-sample
result	HPV positive on a self-	

	sample and histological confirmation of CIN2+	
To assess the logistics of testing samples, recording results and giving women their results in a timely manner.	testing and results	
Exploratory Objectives	propurage GPs to offer self-s	campling opportunistically to women who are overdue cervical screening consult

To pilot a variety of approaches to encourage GPs to offer self-sampling opportunistically to women who are overdue cervical screening consult for any reason. Where GP functionality exists text message ordering will also be utilised, but it is unclear how many GP sites will have the functionality to offer this. Availability of additional services will be recorded to see if this is a viable method to take forward into future work

To pilot a variety of approaches to facilitating women who wish to order a self-sampling kit

To compare demographic and cervical screening status (never screened, overdue, up-to-date) between responders and non-responders

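### Opportunistic uptake divides laboratory returns by GP-coded offers without linking the two, so it reads too high to the extent that offers go uncoded

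*Protocol*

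**What the plan says.** Primary objective (i) is the proportion of women who provide a self-sample when offered a kit opportunistically. Appendix 1 defines the numerator as "Opportunistic: number of eligible women with self-sample returned (using" laboratory data. The full clause then runs "data provided by lab) as a % of total eligible women with Read codes for kits" offered, as found in GP records. The numerator therefore comes from the laboratory and the denominator from practice coding.

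The offer code depends on a template. Section 5.2.1 states: "When eligible women are offered kits, the consulting health professional will use the template to record" whether the kit was accepted, the "Study kit number (if accepted") and any reason for declining. Section 10.3 adds: "Consent to accept a self-sampling kit will be recorded in the women's GP medical record".

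Section 8.2, under the opportunistic arm, gives another source. It introduces its four proportions, the last being return of an adequate sample, with "Using electronic GP record searches: The proportion of eligible women who". Under Section 7.2, HPV results reach the GP record only when practice administrative staff enter them as Read codes.

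A returned kit can be recognised as opportunistic without any template entry, because Section 6.1.1 says "PSL will maintain a log of what 'SK' numbers were sent to each site".

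**The concern.** The laboratory sees every kit posted back. The GP search sees only offers that someone entered in the template. Appendix 1 neither states that the first group must lie inside the second nor says what to do with a returned kit that has no offer code. Followed as written, a missed offer code lowers the denominator and leaves the numerator untouched.

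Missed entries are plausible. The template is completed around a short conversation at the end of a consultation, and Section 10.3 itself describes consultations as averaging 9 minutes.

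Two comparisons are exposed. Appendix 1 sets the three routes side by side, and the two mailed routes use women sent a kit or a letter as denominators, which do not depend on template coding. Section 8.2 also plans to examine uptake by practice, so a practice that codes poorly would appear to have higher uptake.

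**Working it through.** **Inputs.** Section 8.1.1 plans about 4000 eligible women in six intervention practices, of whom 60% consult. Of those consulting, it expects "500 (21%) will be opportunistically offered a self-sampling kit", about 330 (14%) to accept and about 210 (9%) to return a sample. The protocol gives no share of offers or hand-outs that go uncoded; the values of u below are assumptions.

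**Reproducing the plan's counts.** 4000 × 0.60 = 2400 consulting. Then 2400 × 0.21 = 504, 2400 × 0.14 = 336 and 2400 × 0.09 = 216, in line with the rounded 500, 330 and 210.

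**True uptake on the Appendix 1 denominator.** 210/500 = 42.0%. Treating women as independent, the 95% half-width is 1.96 × √(0.42 × 0.58/500) = 4.3 points.

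**Case A: a share u of accepted hand-outs is uncoded, all declines are coded, and uncoded kits have the same return rate.** Coded offers are 500 − 330u.

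- As written: 210/(500 − 330u).
- Linked (returners must be coded offers): 210(1 − u)/(500 − 330u).
- Sensitivity (unmatched returners added to both linked counts): 210/(500 − 330u + 210u).

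| u | As written | Linked | Sensitivity |
|---|---|---|---|
| 0% | 42.0% | 42.0% | 42.0% |
| 5% | 210/483.5 = 43.4% | 199.5/483.5 = 41.3% | 210/494 = 42.5% |
| 10% | 210/467 = 45.0% | 189/467 = 40.5% | 210/488 = 43.0% |
| 20% | 210/434 = 48.4% | 168/434 = 38.7% | 210/476 = 44.1% |

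At u = 10%, 33 hand-outs are uncoded. About 21 are returned and enter the numerator only; about 12 are not returned and enter neither count. The share entering the numerator alone is 210/330 = 64%.

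**Case B: a share u of all offers is uncoded, whatever the outcome.** Coded offers are 500(1 − u).

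| u | As written | Linked | Sensitivity |
|---|---|---|---|
| 5% | 210/475 = 44.2% | 42.0% | 43.3% |
| 10% | 210/450 = 46.7% | 42.0% | 44.6% |
| 20% | 210/400 = 52.5% | 168/400 = 42.0% | 210/442 = 47.5% |

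**Case C: only declines go uncoded.** There are 500 − 330 = 170 declines. At u = 20% the denominator is 500 − 34 = 466, and all three calculations give 210/466 = 45.1%, because every returner is coded and nothing is unmatched.

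The as-written ratio is too high in all three cases. Linking removes the bias in Case B, over-corrects in Case A and does nothing in Case C.

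**The case against.** The best defence is that a linked count was meant. A percentage of a group normally implies a subset, the numerator is limited to eligible women, and eligibility is read from GP records, so a bare laboratory list could not produce it. The template captures the kit number, which is a natural link. Section 9.2 gives the team line-level GP data for women who return a sample, and Section 13 provides for audit of consent recording and data quality. Exact linkage rules often sit in a statistical analysis plan, which is not at hand.

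Part of this stands: the means of linking exist. But eligibility is not the same as having an offer code, so restricting to eligible women does not put the numerator inside the denominator. Nor is this only missing detail, because the protocol fixes a source for each count and leaves the two unmatched. It is fair to say that the line in Section 8.2 concerns adequate samples among all eligible women, a different proportion from Appendix 1. It still draws returns from a different source, and that needs reconciling.

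A reader might infer three stronger things that the protocol does not support. First, that every uncoded hand-out inflates the numerator: only those returned do, about 64% on the planned figures. Second, that the estimate is certainly too high: each offer is supposed to be recorded, no uncoded rate is given, and complete coding gives no bias. Third, that women who leave the practice are lost from one final search: the timing of the offer searches is not stated.

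The effect should also be kept in proportion. In Case A, at 5% to 10% uncoded, the error is 1.4 to 3.0 points, inside the half-width. Section 8.2 says this pilot has no formal primary outcome measure, and the chi-square test named in the synopsis compares only the individually randomised arms.

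**Conclusion.** The concern holds in conditional form. As written, the Appendix 1 ratio for opportunistic uptake is biased upward to the extent that offers go uncoded, and only this one of the three primary proportions is affected. If hand-outs alone go uncoded, the planned 42.0% would read 43.4%, 45.0% or 48.4% at 5%, 10% or 20%. The error at 20%, 6.4 points, exceeds the 4.3-point half-width; the smaller ones do not. These sizes rest on an assumed uncoded share, an equal return rate for coded and uncoded kits, and independence between women. The actual size cannot be determined from the protocol. The difference between Appendix 1 and Section 8.2 over the source of returns stands whatever the coding rate.

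**What to change.** In Appendix 1 and Section 8.2:

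- Name laboratory data as the one source of returns, and amend the opportunistic-arm text in Section 8.2 to agree.
- Define the numerator as women whose returned kit is linked by kit (SK) number to a coded offer, so that it lies inside the denominator.
- Report, by practice, the returned kits that appear on an intervention practice's SK log but have no offer code.
- Give a sensitivity estimate that adds those women to both numerator and denominator.

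State the limits alongside. The linked estimate can be too low if only hand-outs go uncoded (38.7% at 20%). The sensitivity estimate is then too high (44.1% at 20%), because it admits uncoded women only when they return a sample. Neither recovers uncoded declines, so the two figures do not always bracket the truth.

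The cost is wording in two places and a little linkage work with data the protocol already collects: the kit number in the template, the SK log and the laboratory returns. No extra participants are needed. Where offers have been missed, reported uptake will be slightly lower than under the present definition.
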